6.3.1.1 Unacceptable Toxicities

The unacceptable toxicity criteria will be any of the following unless clearly related to an alternative cause other than study drug:

- Grade 5 toxicity
- Grade 4 non-hematologic toxicity (not laboratory)
- Grade 4 hematologic toxicity lasting ≥ 7 days
- Grade 3 non-hematologic toxicity (not laboratory) lasting >3 days despite optimal supportive care
- Any Grade 3 or Grade 4 non-hematologic laboratory value if:
 - Medical intervention is required to treat the subject,
or
 - The abnormality leads to hospitalization, or
 - The abnormality persists for >1 week
- Grade 3 or 4 febrile neutropenia
 - Grade 3 is defined as $\text{ANC} < 1000/\text{mm}^3$ with a single temperature of $>38.3^\circ\text{C}$ (101°F) or a sustained temperature of $\geq 38^\circ\text{C}$ (100.4°F) for more than one hour
 - Grade 4 is defined as $\text{ANC} < 1000/\text{mm}^3$ with a single temperature of $>38.3^\circ\text{C}$ (101°F) or a sustained temperature of $\geq 38^\circ\text{C}$ (100.4°F) for more than one hour, with life-threatening consequences and urgent intervention indicated
- Thrombocytopenia $< 25,000/\text{mm}^3$ if associated with:
 - A bleeding event which does not result in hemodynamic instability but requires an elective platelet transfusion,
or
 - A life-threatening bleeding event which results in urgent intervention and admission to an Intensive Care Unit
- Delay of >8 days starting Cycle 2 due to study drug-related toxicity
- Administration of systemic steroids to treat an immune-mediated reaction
- Serum chemistry laboratory values consistent with Hy's Law criteria (i.e. all 3 of the following must coexist):
 - ALT or AST $\geq 3 \times \text{ULN}$
 - Total bilirubin $\geq 2 \times \text{ULN}$
 - ALP $< 2 \times \text{ULN}$

Safety data and all unacceptable toxicities will be reviewed by the SRT comprised of participating investigators in the study, the Medical Monitor, and Sponsor representatives. Once the Safety Run-in is complete, safety will continue to be evaluated on an ongoing basis in this open-label study. Cumulative clinical experience with CRS-207 and pembrolizumab will be used to assess whether AEs are considered expected.

Subjects who experience an unacceptable toxicity directly attributable to either pembrolizumab or CRS-207 may continue on study and receive either pembrolizumab or CRS-207 as single agent treatment following completion of the Sponsor Consultation Form and approval by the Medical Monitor. Alternatively, study drug administration may revert back to consecutive day-dosing regimen as performed in Cycle 1.

6.3.2 Method of Assigning Subjects to Treatment

All subjects will be sequentially assigned a unique subject identification number upon providing informed consent. The study is designed as a single-arm study; all subjects will receive CRS-207/pembrolizumab as indicated.

6.3.3 Blinding

ADU-CL-14 is a single-arm, open-label study. Due to the expected infusion-related reactions and required pre-medications associated with CRS-207 administration, and since all subjects receive the same study drugs, it is not feasible or necessary to conduct the study under blinded conditions. All study treatments will be administered open-label; no study participants or site personnel will be blinded to study treatment.

6.3.4 Investigational Product: CRS-207

CRS-207 is a LADD strain derived by deletion of *actA* and *inlB* coding sequences from a streptomycin-resistant, wild-type strain and insertion of the *hMeso* coding sequence. The CRS-207 drug product is formulated as 1×10^9 CFU suspended in [REDACTED]

[REDACTED], filled into a single-use 2-mL glass vial with a gray butyl stopper and aluminum crimp seal with a flip-off cap. CRS-207 is stored frozen at -60 °C or colder until just before IV administration. CRS-207 is supplied by the Sponsor. Additional information on CRS-207 may be found in the Pharmacy Manual and IB.

6.3.4.1 Biosafety and Environmental Precautions

In wild-type form, *Lm* is a bacterium commonly found in soil and water, and may be present in a variety of raw and processed foods. Listeriosis is a foodborne illness caused by wild-type *Lm* which primarily affects pregnant women and immunocompromised individuals. Direct human-to-human spread of *Lm* is believed to be limited mainly to vertical transmission from mother to neonate. CRS-207 is a LADD construct originating from wild-type *Lm* which contains deletions of 2 virulence genes that render it greater than 1000-times less toxic than wild-type *Lm* in mice (Brockstedt, 2004).

LADD-based immunotherapies (*Lm* Δ *actA*/ Δ *inlB*) including CRS-207, have been designated as Risk Group 1 by the Aduro Institutional Biosafety Committee. Risk Group 1 is consistent with the guidance by the German ZKBS (Central Commission for Biological Safety) for classification of *Lm* strains with deletion in genes *prFA*, *hly*, *actA*, and *plcB* (BVL, 1999). Individuals who prepare CRS-207 for infusion must take appropriate precautions (e.g. gloves, laboratory coat,

face protection, needle stick or sharps precautions) to avoid contamination or direct contact with the agent. Once prepared for infusion, the chance for direct exposure to CRS-207 by study personnel should be greatly diminished. However, study personnel and staff should continue to adhere to the institutional guidelines for standard precautions.

Based on nonclinical studies and available clearance and shedding data from clinical studies, a subject who receives CRS-207 is unlikely to spread an infection to others. Subjects receiving CRS-207 should be counseled to minimize the potential risk of spreading CRS-207 by practicing good health hygiene (e.g. hand-washing) as with any potential infectious agent, and adhering to protocol requirements for barrier method of contraception during sexual intercourse.

6.3.4.2 CRS-207 Administration

CRS-207 is intended for IV administration. The intended dose of CRS-207 is 1×10^9 CFU diluted in sterile saline and administered by IV infusion. Additional details for storage and preparation of CRS-207 are provided in the study Pharmacy Manual.

Use of Central Lines

To avoid contamination of a central line (e.g. infusion ports, peripherally inserted central catheter) with CRS-207 during and after infusion:

- CRS-207 must **NOT** be administered through a central line or infusion ports
- Central lines must **NOT** be used or accessed for any reason once CRS-207 infusion has been initiated (including blood draws, medication administration or line flushing; blood draws prior to infusion through a port or central line are allowed) and through 4 days after infusion
- Central lines must be clearly labeled with tape or other method indicating date when port may be used again after CRS-207 infusion

Pre-Medication and Post-Infusion Observation

Before each CRS-207 infusion, subjects should be pre-medicated with 650 mg (or maximum dose permitted by label) acetaminophen (paracetamol). Adequate hydration is important to mitigate infusion-related reactions. All subjects are required to receive a minimum of 0.5 L of normal saline immediately before CRS-207 infusion; an additional 0.5 - 1 L after infusion is recommended, as tolerated. Additional fluids may be given for persistent tachycardia, fever, or hypotension based on Investigator's discretion.

Subjects will be observed in the clinic for at least 4 hours after the first CRS-207 infusion. For Same-day dosing on Cycle 2 only, observe subjects for at least 4 hours. For all subsequent infusions observe subjects for at least 2 hours post infusion. Subjects should continue to be monitored after infusion and released once they are considered clinically stable. Vital signs and pulse oximetry will be monitored ([Section 6.4.3.1](#)). Presence of fever alone in the absence of other clinical signs and symptoms does not preclude the subject from being released. Hospital

admissions for overnight monitoring will not be considered an SAE unless the event meets criteria for seriousness other than hospitalization.

During and after CRS-207 infusions, subjects may experience fever, chills/rigor, blood pressure changes, nausea, and vomiting. Refer to [Section 6.3.7](#) and the IB for additional details on CRS-207 administration and supportive care.

6.3.4.3 CRS-207 Dose Modification

CRS-207 at the proposed dose level has been well tolerated and dose reductions are not anticipated. However, in the event of AEs of concern that are attributable to CRS-207 the Medical Monitor should be contacted; the dose of CRS-207 may also be modified outside the Safety Run-in Period as warranted on an individual basis.

6.3.5 Investigational Product: Pembrolizumab

Pembrolizumab is a humanized monoclonal antibody that blocks the interaction between PD-1 and its ligands, PD-L1 and PD-L2. Pembrolizumab is an IgG4 kappa immunoglobulin with an approximate molecular weight of 149 kDa. Pembrolizumab is not currently approved for treatment of gastric, GEJ, or esophageal adenocarcinomas and is being used as an investigational agent in this study. However, the approved package insert should be consulted for additional product information on storage, preparation and administration, contraindications, warnings/precautions, adverse reactions, and drug interactions.

Pembrolizumab for injection is a sterile, preservative-free, clear to slightly opalescent, colorless to slightly yellow solution that requires dilution for IV infusion. Each vial contains 100 mg of pembrolizumab in 4 mL of solution. Each 1 mL of solution contains 25 mg of pembrolizumab and is formulated in: L-histidine (1.55 mg), polysorbate 80 (0.2 mg), sucrose (70 mg), and Water for Injection, USP.

6.3.5.1 Pembrolizumab Administration

Pembrolizumab will be diluted and administered as a dose of 200 mg using a 30-minute IV infusion. Sites should target infusion timing to be as close to 30 minutes as possible. However, given the variability of infusion pumps, a window between -5 minutes and +10 minutes is permitted (i.e. infusion time is 30 minutes -5 min/+10 min). Do not co-administer other drugs through the same infusion line. Pembrolizumab infusions will be administered Q3W for up to 24 months. The Pharmacy Manual contains specific instructions for the preparation of the pembrolizumab infusion and administration of infusion solution.

Pembrolizumab Supportive Care Guidelines

Subjects should receive appropriate supportive care measures as deemed necessary by the investigator. Suggested supportive care measures for the management of pembrolizumab-related AEs with potential immunologic etiology along with dose modification guidelines are outlined below. Where appropriate, these guidelines include the use of oral or IV treatment with

corticosteroids as well as additional anti-inflammatory agents if symptoms do not improve with administration of corticosteroids. Several courses of steroid tapering may be necessary as symptoms may worsen when the steroid dose is decreased. For each disorder, attempts should be made to rule out other causes such as metastatic disease or bacterial or viral infection, which might require additional supportive care. The treatment guidelines are intended to be applied when the Investigator determines the events to be related to pembrolizumab.

Note: If the event is determined not to be related to pembrolizumab, the Investigator does not need to follow the treatment guidance (as outlined below). It may be necessary to perform conditional procedures such as bronchoscopy, endoscopy, or skin photography as part of evaluation of the event.

6.3.5.2 Pembrolizumab Dose Modification and Toxicity Management

Immune-related Adverse Events Associated with Pembrolizumab

AEs associated with pembrolizumab exposure may represent an immunologic etiology. These immune-related AEs (irAEs) may occur shortly after the first dose or several months after the last dose of pembrolizumab treatment and may affect more than one body system simultaneously. Therefore, early recognition and initiation of treatment is critical to reduce complications. Based on existing clinical trial data, most irAEs were reversible and could be managed with interruptions of pembrolizumab, administration of corticosteroids and/or other supportive care. For suspected irAEs, ensure adequate evaluation to confirm etiology or exclude other causes. Additional procedures or tests such as bronchoscopy, endoscopy, skin biopsy may be included as part of the evaluation. Based on the severity of irAEs, withhold or permanently discontinue pembrolizumab and administer corticosteroids.

Dose modification and toxicity management guidelines for irAEs associated with pembrolizumab are provided in [Table 6-4](#). The Medical Monitor will be consulted regarding continued dosing of CRS-207 should any of these events occur. During the Safety Run-in Period withholding pembrolizumab or administering systemic steroids would define an unacceptable toxicity.

Table 6-4 Dose Modification and Toxicity Management Guidelines for Immune-Related Adverse Events Associated with Pembrolizumab

General Instructions:				
Immune-related AEs	Toxicity grade or conditions (CTCAEv4.0)	Action taken to pembrolizumab	irAE management with corticosteroid and/or other therapies	Monitor and follow-up
Pneumonitis	Grade 2	Withhold	
 Administer corticosteroids (initial dose of 1-2mg/kg prednisone or equivalent) followed by taper 	
 Monitor subjects for signs and symptoms of pneumonitis Evaluate subjects with suspected pneumonitis with radiographic imaging and initiate corticosteroid treatment Add prophylactic antibiotics for opportunistic infections
	Grade 3 or 4, or recurrent grade 2	Permanently discontinue		
Diarrhea / colitis	Grade 2 or 3	Withhold	
 Administer corticosteroids (initial dose of 1-2mg/kg prednisone or equivalent) followed by taper 	
 Monitor subjects for signs and symptoms of enterocolitis (i.e. diarrhea, abdominal pain, blood or mucus in stool with or without fever) and of bowel perforation (i.e. peritoneal signs and ileus). Subjects with \geq Grade 2 diarrhea suspecting colitis should consider GI consultation and performing endoscopy to rule out colitis. Subjects with diarrhea/colitis should be advised to drink liberal quantities of clear fluids. If sufficient oral fluid intake is not feasible, fluid and electrolytes should be substituted via IV infusion.
	Grade 4	Permanently discontinue		

AST / ALT elevation or Increased Bilirubin	Grade 2	Withhold	
 Administer corticosteroids (initial dose of 0.5- 1mg/kg prednisone or equivalent) followed by taper 	
 Monitor with liver function tests (consider weekly or more frequently until liver enzyme value returned to baseline or is stable)
	Grade 3 or 4	Permanently discontinue	
 Administer corticosteroids (initial dose of 1-2mg/kg prednisone or equivalent) followed by taper 	
Type 1 diabetes mellitus (T1DM) or Hyperglycemia	Newly onset T1DM or Grade 3 or 4 hyperglycemia associated with evidence of β -cell failure	Withhold	
 Initiate insulin replacement therapy for subjects with T1DM Administer anti-hyperglycemic in subjects with hyperglycemia 	
 Monitor subjects for hyperglycemia or other signs and symptoms of diabetes.
Hypophysitis	Grade 2	Withhold	
 Administer corticosteroids and initiate hormonal replacements as clinically indicated. 	
 Monitor for signs and symptoms of hypophysitis (including hypopituitarism and adrenal insufficiency)
	Grade 3 or 4	Withhold or permanently discontinue ¹		
Hyperthyroidism	Grade 2	Continue	
 Treat with non-selective beta-blockers (e.g. propranolol) or thionamides as appropriate 	
 Monitor for signs and symptoms of thyroid disorders.
	Grade 3 or 4	Withhold or Permanently discontinue ¹		
Hypothyroidism	Grade 2-4	Continue	
 Initiate thyroid replacement hormones (e.g. levothyroxine or liothyroinine) per standard of care 	
 Monitor for signs and symptoms of thyroid disorders.
Nephritis and renal dysfunction	Grade 2	Withhold	
 Administer corticosteroids (prednisone 1-2mg/kg or equivalent) followed by taper. 	
 Monitor changes of renal function
	Grade 3 or 4	Permanently discontinue		

All Other immune-related AEs	Grade 3, or intolerable/ persistent Grade 2	Withhold	
• Based on severity of AE administer corticosteroids	
• Ensure adequate evaluation to confirm etiology or exclude other causes
	Grade 4 or recurrent Grade 3	Permanently discontinue		

NOTES:

1. Withhold or permanently discontinue pembrolizumab is at the discretion of the investigator or treating physician.
2. For subjects with Grade 3 or 4 immune-related endocrinopathy where withhold of pembrolizumab is required, pembrolizumab may be resumed when AE resolves to \leq Grade 2 and is controlled with hormonal replacement therapy or achieved metabolic control (in case of T1DM).

Infusion Reactions Related to Pembrolizumab

Pembrolizumab may cause severe or life threatening infusion-reactions including severe hypersensitivity or anaphylaxis. Signs and symptoms usually develop during or shortly after drug infusion and generally resolve completely within 24 hours of completion of infusion. Dose modification and toxicity management guidelines on pembrolizumab associated infusion reaction are provided in Table 6-5.

Table 6-5 Pembrolizumab Infusion Reaction Dose Modification and Treatment Guidelines

NCI CTCAE Grade	Treatment	Premedication at Subsequent Dosing
Grade 1 Mild reaction; infusion interruption not indicated; intervention not indicated	Increase monitoring of vital signs as medically indicated until the subject is deemed medically stable in the opinion of the investigator.	None
Grade 2 Requires therapy or infusion interruption but responds promptly to symptomatic treatment (e.g., antihistamines, NSAIDs, narcotics, IV fluids); prophylactic medications indicated for ≤ 24 hrs	
Stop Infusion.
 
Additional appropriate medical therapy may include but is not limited to:
 
IV fluids Antihistamines NSAIDs Acetaminophen Narcotics
 
Increase monitoring of vital signs as medically indicated until the subject is deemed medically stable in the opinion of the investigator.
 
If symptoms resolve within 1 hour of stopping drug infusion, the infusion may be restarted at 50% of the original infusion rate (e.g. from 100 mL/hr to 50 mL/hr). Otherwise dosing will be held until symptoms resolve and the subject should be premedicated for the next scheduled dose.
 
Subjects who develop Grade 2 toxicity despite adequate premedication should be permanently discontinued from further study drug treatment
	
Subject may be premedicated 1.5h (\pm 30 minutes) prior to infusion of pembrolizumab with:
 
Diphenhydramine 50 mg po (or equivalent dose of antihistamine).
 
Acetaminophen 500-1000 mg po (or equivalent dose of analgesic).

NCI CTCAE Grade	Treatment	Premedication at Subsequent Dosing
Grades 3 or 4 Grade 3: Prolonged (i.e., not rapidly responsive to symptomatic medication and/or brief interruption of infusion); recurrence of symptoms following initial improvement; hospitalization indicated for other clinical sequelae (e.g., renal impairment, pulmonary infiltrates) Grade 4: Life-threatening; pressor or ventilatory support indicated	Stop Infusion. Additional appropriate medical therapy may include but is not limited to: Epinephrine** IV fluids Antihistamines NSAIDs Acetaminophen Narcotics Oxygen Pressors Corticosteroids Increase monitoring of vital signs as medically indicated until the subject is deemed medically stable in the opinion of the investigator. Hospitalization may be indicated. **In cases of anaphylaxis, epinephrine should be used immediately. Subject is permanently discontinued from further study drug treatment.	No subsequent dosing

Appropriate resuscitation equipment should be available at the bedside and a physician readily available during the period of drug administration.

[figure not shown]
For further information, please refer to the Common Terminology Criteria for Adverse Events v4.0 (CTCAE) at <http://ctep.cancer.gov>

Other Allowed Dose Interruptions for Pembrolizumab

Pembrolizumab may be interrupted for situations other than treatment-related AEs such as medical / surgical events or logistical reasons not related to study therapy. Subjects should be placed back on study therapy within 3 weeks of the scheduled interruption, unless otherwise discussed with the Sponsor. The reason for interruption should be documented in the subject's study record.

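### Withholding pembrolizumab in the Safety Run-in is an unacceptable toxicity in Protocol 6.3.5.2 but is missing from the 6.3.1.1 criteria that feed the 4-in-12 dose-reduction rule

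*Protocol*

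**What the plan says.** Protocol 6.3.1 reduces CRS-207 by a half-log if 4 of up to 12 safety-evaluable subjects have an unacceptable toxicity within the 28-day window. The synopsis, Protocol 6.1 and SAP 3.1 give the same rule.

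The events are defined in Protocol 6.3.1.1, which opens: "The unacceptable toxicity criteria will be any of the following unless clearly related to an alternative cause other than study drug". Two of its items bear on this point: "Administration of systemic steroids to treat an immune-mediated reaction" and "Delay of >8 days starting Cycle 2 due to study drug-related toxicity". No item concerns withholding pembrolizumab. Protocol 6.2.4.1 refers to this section by number for its stopping rules.

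Protocol 6.3.5.2, which introduces the management table for immune-related events (Table 6-4), adds: "During the Safety Run-in Period withholding pembrolizumab or administering systemic steroids would define an unacceptable toxicity". Of the two triggers in that sentence, only the steroid one appears in 6.3.1.1, and neither section refers to the other on this matter.

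**The concern.** The run-in rule depends on a small count, so the definition of an event has to be the same wherever it is stated. Here two operative sections differ. Someone who tallies from 6.3.1.1 would not count a subject whose pembrolizumab was held and who met no listed criterion. Someone who follows 6.3.5.2 would. If a cohort has three listed events and one such hold, the first tally gives 3 and leaves the dose unchanged, while the second gives 4 and lowers it. The protocol itself gives the lack of prior data on this combination as the reason for the run-in.

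**Working it through.** **Step 1. The plan's own threshold.** 4/12 = 33.3%, which agrees with the stopping rule of more than 33% in Protocol 6.2.4.1. The documents state no target toxicity rate or error rate for the rule, so there is no operating characteristic to reproduce.

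**Step 2. Which holds in Table 6-4 are already counted through 6.3.1.1.**

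- Pneumonitis, diarrhea/colitis, liver test elevation, hypophysitis and nephritis: the hold comes with corticosteroids, so the steroid criterion is met.
- Grade 3 or 4 hyperthyroidism: no steroids are specified, but Grade 4, or Grade 3 lasting more than 3 days despite supportive care, is listed.
- Diabetes row ("Newly onset T1DM or Grade 3 or 4 hyperglycemia"): treatment is insulin or anti-hyperglycemic drugs, not steroids. Grade 3 or 4 glucose that needs medical intervention is listed. New type 1 diabetes with glucose below Grade 3 need not meet any listed item.
- All other immune-related events: Grade 3, or intolerable or persistent Grade 2, calls for a hold, and steroids are conditional ("Based on severity of AE administer corticosteroids"). Grade 3 lasting more than 3 days is listed. Grade 2 managed without steroids is not.

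**Step 3. Timing.** With 3-week cycles and a 28-day window, the Cycle 2 dose is the only pembrolizumab dose after the first that can be held inside the window. A toxicity-related delay of more than 8 days in starting Cycle 2 is listed. What remains is a steroid-free hold, mainly of the two kinds in Step 2, with Cycle 2 delayed by 8 days or less.

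**Step 4. Illustration only.** Let p be the rate of listed events and q the added rate of hold-only events. Neither is in the documents; both are assumed. With 12 independent evaluable subjects,

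P(X ≥ 4) = 1 − Σ(k = 0 to 3) C(12,k) r^k (1 − r)^(12−k),

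with r = p if holds do not count and r = p + q if they do. At p = 0.20, 1 − (0.0687 + 0.2062 + 0.2835 + 0.2362) = 0.205.

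| p | Holds not counted | q = 0.01 | q = 0.02 | q = 0.05 |
|---|---|---|---|---|
| 0.15 | 0.092 | 0.111 | 0.132 | 0.205 |
| 0.20 | 0.205 | 0.233 | 0.261 | 0.351 |
| 0.25 | 0.351 | 0.382 | 0.414 | 0.507 |

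Every listed event counts under both readings, so the difference from the second column is the share of 12-subject cohorts in which the two give different decisions. It is 0.019 to 0.063 for q of 0.01 to 0.02. Because so little is left after Steps 2 and 3, the low end of q is the more plausible.

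**The case against.** The best reply is that the sections can be read together. Protocol 6.3.1.1 does not say that its list is exclusive. Protocol 6.3.5.2 is operative text that expressly adds a run-in criterion, while 6.2.4.1 applies 6.3.1.1 throughout the study. On that reading a hold-only subject counts and only a cross-reference is missing. This reading is available, but the text does not require it. The 6.3.1.1 list is introduced as the criteria, repeats the steroid trigger, leaves out its companion and sends the reader nowhere else.

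It is also fair to say that the residue is very small, that any trigger probability merely restates the assumed rates, and that the consequence now is slight. All three stand.

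Two stronger readings are tempting, and the documents do not support them.

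- A reader might infer that the single-agent provision lets a subject start Cycle 2 on time with CRS-207 alone and go uncounted. That provision says subjects "may continue on study and receive either pembrolizumab or CRS-207 as single agent", but only if they have already had an unacceptable toxicity, so such a subject is an event by definition. The other relevant sentence, "The Medical Monitor will be consulted regarding continued dosing of CRS-207 should any of these events occur", leaves CRS-207 dosing open and does not say that it would proceed.
- A reader might infer that the run-in size is itself in dispute, because Protocol 4.3 speaks of the first 6 subjects. The synopsis, Protocol 6.1 and 6.3.1, and SAP 3.1 all use up to 12 and give the first 6 only a staggered start. The sentence in 4.3 is background text and needs only a clerical correction.

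**Conclusion.** The inconsistency is present in the current text, and it is minor. One section makes a pembrolizumab hold in the run-in an unacceptable toxicity, and the list behind the dose-reduction rule does not. The subjects affected are few: mainly those with a persistent or intolerable Grade 2 event in the residual row of Table 6-4, or new type 1 diabetes with glucose below Grade 3, without steroids and with Cycle 2 no more than 8 days late.

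Its effect on the rule cannot be estimated from the documents. The differences of about 2 to 6 percentage points in the illustration rest wholly on assumed base rates of 15% to 25% and assumed hold-only rates of 1 to 2 points, and are not a finding about this trial.

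Nothing in the documents shows that a dose decision was wrong. SAP 3.5 records that every subject had completed the end-of-treatment visit by 31 January 2018, so none can change now. No summary table or estimate is affected. SAP 10.1 places unacceptable toxicities in the adverse event listing without naming the definition or saying how they are identified, so at most that flag could differ for a hold-only subject.

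**What to change.** Add to Protocol 6.3.1.1: 'pembrolizumab withheld for an immune-related AE per Table 6-4 during the 28-day Safety Run-in window'. Replace the sentence in 6.3.5.2 with a reference to that list. Naming immune-related events keeps administrative interruptions out, and naming the window keeps the criterion from extending to the whole study through 6.2.4.1. As a clerical matter, align the sentence in 4.3 with up to 12 safety-evaluable subjects, the first 6 staggered. With the study closing, the practical equivalent is one sentence in SAP 10.1 stating which definition the listing flag uses.

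The change is wording only, with no added visits or data. It has one real cost: immune-related holds of 8 days or less would count, although 6.3.1.1 otherwise tolerates a Cycle 2 delay of that length. In a run-in still under way this would slightly raise the chance of a CRS-207 reduction, by an amount the documents do not allow one to estimate. Deleting the withholding phrase from 6.3.5.2 would also reconcile the sections, but it would remove a safety criterion that the protocol states outright.
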